9.4.2. Week 12 (Secondary Outcomes) (+/- 7 days)

As per standard clinical care/T2T, patients will undergo the following routine clinical & laboratory assessments:

- **General**
 - Confirm eligibility and consent
 - Assess compliance with treatment
 - Clinical observations will be performed as per standard care (not required as a research parameter)
 - Medication, allergy and co-morbidity check
- **Clinical assessment data**
 - Joint examination performed by an independent assessor:
 - Tender joint count (28)
 - Swollen joint count (28)
 - Disease activity score (DAS28)
 - Clinical disease activity index (CDAI)
 - Simplified disease activity index (SDAI)
 - Early morning stiffness (mins)
 - Cardio-respiratory examination if clinically indicated
- **Patient reported outcomes**
 - Visual analogue scores of pain/disease activity/general health
 - Physician assessment of general health
 - HAQ-DI
- **Laboratory tests**
 - Routine haematology and biochemistry suitable for diagnostic investigation & therapeutic DMARD monitoring FBC, U&E, LFT & eGFR ml/min/1.73 m²
 - ESR (mm/h) & CRP (mg/L)
 - Urinalysis/pregnancy test if clinically indicated
- **Adverse event recording**

- **DMARD management according to T2T pathway. (Assessment of remission target will be done after 12 weeks of treatment) +/- IM/IA/PO corticosteroids as appropriate (in line with standard practice) .**
- **Document steroid used, dose and method of administration**

9.4.3. Week 24 (Primary Outcome) (+/- 7 days)

- As per week 12 plus:
 - **Imaging** (+/- 7 days from clinic visit):: Power Doppler Ultrasound (PDUS) of standard set of 26 joints and 6 tendons for grey-scale (GS), power Doppler (PD), erosions (E) and osteophytes (O) and tenosynovitis (TSV)
 - Biologic blood sample collection for storage (exploratory biomarkers)
- In line with usual clinical care/T2T, cessation or alteration of treatment regimens at any time will be at the discretion of attending clinicians or the participants themselves.
- All participants withdrawn from treatment(s) will still attend for follow-up assessments and questionnaires and CRFs will continue to be completed.

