1.2.2.2 Supportive medication

Folic Acid: Patients taking MTX will be co-prescribed oral folic acid as per standard care in our T2T clinic (5mg daily, 6 days per week, except day of MTX).

Administration of IMP' & non-IMPs:

- For patients with normal baseline naïve CD4⁺ T-cells (Arm A), MTX will be administered as per standard T2T care at a starting dose of 15mg/week PO*. If tolerated, dose escalation will occur at follow-up in line with our T2T schedule.
- Patients with abnormal baseline naïve CD4⁺ T-cells will be randomized to receive either MTX 15mg/week PO* (Arm B) or MTX 15mg/week PO* + Benepali® 50mg SC injection, as per licenced use (Arm C). Follow-up of patients in both arms and dose escalation of MTX will also occur in line with our T2T schedule.
- The treating physician will have been monitoring patients for side effects from the beginning of their treatment. Side effects will be monitored by clinical assessment and by blood testing at each study visit.

**(or SC as per standard practice – see section 7.3 for further guidance)*

Rescue medication/treatment of flare

- Patients in either study arm may receive corticosteroid treatment (IM/IA or oral) at any of the follow-up study visits or at unscheduled visits if they have evidence of clinical flare i.e. do not meet target DAS28ESR<2.6. Administered doses will be in line with local standard clinical practice. For patients meeting the target DAS score, however have evidence of flare i.e. synovitis as per the assessing physician, corticosteroids may be offered. Administration of this will be logged in the CRF.
- Small doses of corticosteroids are relatively safe, with only a small risk of side effects e.g. weight gain, mood and sleep disturbance, which are usually only short-lived.
- Long-term use of high doses is often associated with bone loss and worsening of osteoporosis. Rarely avascular necrosis can occur. Corticosteroids can also transiently cause an increase in blood sugars, necessitating increased blood sugar monitoring/extra caution in diabetic patients. Menstrual disturbance has also been noted.
- Injections can occasionally cause thinning of the skin or depigmentation at the injection site. Intra-articular injections may be associated with increased pain within the joint for 24 hours and rarely joint infection in less than 1:5000 cases. The need for rescue medication will be recorded as an adverse event.

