3.2. Secondary endpoint(s)

- The difference in the proportions of patients in clinical remission (DAS28ESR ≤ 2.6) after 12 weeks of first-line MTX with T2T care between those with normal (Arm A) vs. abnormal (Arm B) naïve CD4 $^{+}$ T-cell frequencies.
- The difference in the proportions of patients in clinical remission (DAS28ESR ≤ 2.6) at 12 & 24 weeks for patients with abnormal baseline naïve CD4 $^{+}$ T-cell frequencies receiving MTX with T2T care (Arm B) vs. etanercept + MTX (Arm C).
- The differences in the medians of patient-reported outcome measures (EMS, VAS scales, HAQ-DI) after 12 & 24 weeks of first-line MTX with T2T care between those with normal (Arm A) vs. abnormal (Arm B) naïve CD4 $^{+}$ T-cell frequencies.
- The differences in the medians of patient-reported outcome measures (EMS, VAS scales, HAQ-DI) after 12 & 24 weeks for patients with abnormal baseline naïve CD4 $^{+}$ T-cell frequencies receiving MTX with T2T care (Arm B) vs. etanercept + MTX (Arm C).
- The difference in the proportions of patients in imaging remission (PD=0) after 24 weeks of first-line MTX with T2T care between those with normal (Arm A) or abnormal (Arm B) naïve CD4 $^{+}$ T-cell frequencies.
- The difference in the proportions of patients in imaging remission (PD=0) at 24 weeks for patients with abnormal baseline naïve CD4 $^{+}$ T-cell frequencies receiving MTX with T2T care (Arm B) vs. etanercept + MTX (Arm C).
- The difference in the proportion of patients with normal naïve CD4 $^{+}$ T-cells at 24 weeks for patients with abnormal baseline naïve CD4 $^{+}$ T-cells receiving MTX with T2T care (Arm B) vs. etanercept + MTX (Arm C).
- The difference in the proportions of patients in sustained clinical remission (DAS28ESR ≤ 2.6) at both 12 and 24 weeks (Arm A vs. Arm B and Arm B vs. Arm C)

- The difference in the average (mean) amount of corticosteroid use at 24 weeks between study arms (Arm A vs. Arm B and Arm B vs. Arm C). This includes any administered at the 24 week visit also.

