5.3. Rationale for study design and selection of dose

- Based on our previous data from both a pilot study and replication cohort, it was observed that reduced naïve CD4⁺ T-cells at baseline could predict remission in DMARD-naïve early RA patients treated with MTX. The association between lower naïve CD4+T-cells and inability to achieve remission was not observed for patients treated with combination MTX + anti-TNF. Therefore, it may be appropriate to consider biologic therapy early in patients with poor prognostic naïve CD4⁺ T-cells. This data suggests that the measurement of T-cell subsets is strongly indicated in clinical practice to facilitate earlier, more targeted treatment [16].
- Subsequently we aimed to conduct a prospective, longitudinal cohort study with an embedded pilot randomised controlled trial to investigate this. An open-label design has been chosen as creation and administration of a placebo is not feasible for this study.

- Methotrexate initiation at 15mg and escalation to 25mg is in line with the standard of care/T2T practice in Leeds. Depo-medrone 120mg injection IM is the standard dose used in Leeds and represents a pragmatic approach to induce rapid suppression of inflammation however, alternative doses, agents and routes of administration may be used as an alternative, as previously described.
- Current product licensing recommends a dose of 50mg/wk subcutaneously for Benepali®.

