8.2. Assessment of secondary efficacy variable(s)

Imaging

- Ultrasound assessment of power doppler synovitis (PD), grey scale (GS) changes, erosions (E) and osteophytes and tenosynovitis will be performed at baseline and 24 weeks, as per our standardised protocol:
 - Standard set of 26 joints:
 - Bilateral wrists
 - Metacarpal joints (MCP) 2 & 3
 - Proximal inter-phalangeal joints (2 & 3)
 - Elbows
 - Knees

- Ankles
- Bilateral metatarsal joints (MTP) 1-5
- Both PD and GS will be scored between 0-3. The scores for individual joints and the totals will be calculated.
- Flexor tendons 2 and 3 bilaterally (MCP and PIP level) and ECU tendons will also be scanned. Both PD and GS will be scored between 0-3 for tenosynovitis.
- Scoring:
 - PD0 = no synovitis
 - PD1 = mild synovitis, ≤3 isolated single areas
 - PD2 = moderate synovitis, >3 isolated singles or confluent signal in less than half of the synovial area
 - PD3 = marked synovitis, signals in more than half of the synovial area
 - GS0 = no grey scale (no synovial hypertrophy)
 - GS1= mild hypoechoic synovial thickening
 - GS2= moderate hypoechoic synovial thickening
 - GS3= marked hypoechoic synovial thickening
- Scans will be performed by the same dedicated ultrasonographer as per other clinical trials within the department.
- It is expected that the scans will take 45 minutes approximately.

Prior to ultrasound, patients will be asked to stop taking any anti-inflammatory drugs (NSAIDs) e.g. ibuprofen for a minimum of 48 hours to maximise the ability for imaging to detect any inflammatory changes present. They will be able to take paracetamol and codeine-based analgesia as an alternative.

Immunological parameters

- A blood sample for T-cell subsets will be taken alongside routine blood tests. These will be processed by the NHS laboratory as it is a standard NHS test in our clinics in Leeds Teaching Hospitals.
- Naïve CD4⁺ T-cells will be measured via cell surface antigen detection by 8-colour flow cytometry. The CD4⁺ T-cells will first be identified by staining for the CD4 and CD45 markers. Naïve cells will be identified based on the high expression of CD45RB and positivity for CD45RA and CD62L. Also included in this panel will be T-regulatory cells

(Treg) and inflammation related cells (IRC's), which may be used at a later date for an exploratory immunological analysis.

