9.3 Baseline visit & IMP commencement (Week 0)*

* Visit to occur within 4 weeks after screening visit

- ***General***

- Confirm eligibility by review of inclusion/exclusion criteria and consent
- Clinical observations will be performed as per standard care (not required as a research parameter)
- Medication, allergy and co-morbidity check

- ***Clinical assessment data***

- Joint examination performed by an independent assessor:
 - Tender joint count (28)
 - Swollen joint count (28)
- Disease activity score (DAS28)
- Clinical disease activity index (CDAI)
- Simplified disease activity index (SDAI)
- Early morning stiffness (mins)
- Cardio-respiratory & abdominal examinations if clinically indicated

- ***Patient reported outcomes***

- Visual analogue scores of pain/disease activity/general health
- Physician assessment of general health
- HAQ-DI

- ***Laboratory tests***

- Routine haematology and biochemistry suitable for diagnostic investigation: FBC, U&E, LFT & eGFR ml/min/1.73 m²

- o ESR (mm/h) & CRP (mg/L)
- o Biologic blood sample collection for storage (exploratory biomarkers)
- o Urinalysis/pregnancy test if clinically indicated

- ***Imaging***

- o Power Doppler Ultrasound (PDUS) of standard set of 26 joints and 6 tendons for grey-scale (GS), power Doppler (PD), erosions (E) and osteophytes (O) and tenosynovitis (TSV) (+/- 7 days from clinic visit)
 - To be performed prior to first administration of study treatments

- ***Adverse event recording***

- ***Initiation of DMARD treatment as per T2T*** (up to 7 days from clinic visit).

- ***Initiation of Benepali® for ARM C*** (up to 7 days from clinic visit).

- o Patients taught how to self-inject

- ***Offer IM/IA/PO corticosteroids as appropriate (in line with standard practice)***

- ***Document steroid used, dose and method of administration***

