12.3. General statistical considerations

Unless otherwise specified, the last valid measurement before study medication administration will be utilized as the baseline value. In general, summary statistics [n (number of available measurements), arithmetic mean, standard deviation, median, minimum, and maximum] for quantitative variables and absolute and relative frequency tables for qualitative data will be presented.

Wherever possible the trial will be reported in accordance with the recommendations of the CONSORT (Consolidated Standards of Reporting Trials) statement.

This trial includes both a confirmatory comparison (arm A vs arm B) and a pilot comparison (arm B vs arm C). For comparisons between arms A and B, two-tailed significance tests will be conducted at the 5% level of significance. Comparisons between arms B and C will be purely descriptive.

A detailed statistical analysis plan (SAP) will be completed prior to the final lock of the database; any differences between the final analysis and the SAP will be documented in the trial report.

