12.9. Determination of sample size and randomization method

We will allocate the patients to arm A if the patient's naive CD4⁺ T-cell frequency is normal for their age and gender. In our previous pilot study 42% of comparable RA patients had abnormal frequency values, of whom 25% responded to MTX at 6 months compared to 68% of those with normal values. Those with abnormal values will be (randomly permuted block) randomised 1:1 to arm B or C, therefore this would result in an approximate 2.75:1 ratio of patients in arms A and B. For the primary outcome of clinical remission at 24 weeks, at the 5% level of significance, to achieve 80% power to detect a difference between the target proportions of patients achieving clinical remission in arms A (68%) and B (25%)[25], a total of 53 patients would be required, assuming binary logistic regression with a variance inflation factor of 1.05 estimated from pilot data. We will increase the sample size to n=60 to account for 10% drop-out. The total number needed to be recruited to the study would therefore be 76 (44 in arm A, 16 in arm B and 16 in arm C).

To have a more robust estimate of the proportion of clinical remission in arm B and C, recruitment will continue until at least 34 and no more than 60 patients with abnormal T-cell values have been randomised 1:1 to arm B or C, and there are at least 46 patients in arm A. Thus the total sample size for the study is anticipated to be between 76 (approximately A=44, B=16, C=16) and 106 patients (approximately A=46, B=30, C=30). In the case where recruitment within Arm A is disproportionately recruiting more than Arm B or C, recruitment will stop within Arm A once minimum recruitment number has been reached. Patients will not be disadvantaged as they will still receive Treat to Target care.

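### The Week 24 power Doppler scan may follow a corticosteroid given at the Week 24 visit, and no rule sets the order or handles such scans

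*Protocol*

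**What the plan says.** - **Visit content.** Protocol 9.4.3 takes over the Week 12 procedures, and 9.4.2 includes optional intramuscular, intra-articular or oral corticosteroid among them. To these it adds the ultrasound; after a plus-or-minus sign the entry reads "7 days from clinic visit):: Power Doppler Ultrasound (PDUS) of standard set of 26 joints and 6 tendons". A footnote to the schedule in 9.1 repeats the window.
- **Steroid at Week 24 is foreseen.** The corticosteroid endpoint in Protocol 3.2 adds: "This includes any administered at the 24 week visit also". SAP 7.2.6 does the same.
- **Trigger.** Under Protocol 1.2.2.2, patients may receive steroid "if they have evidence of clinical flare i.e. do not meet target DAS28ESR<2.6". It may also be offered to patients at target whom the physician judges to have synovitis.
- **Anti-inflammatory treatment and imaging.** Protocol 8.2 stops NSAIDs before ultrasound "for a minimum of 48 hours to maximise the ability for imaging to detect any inflammatory changes present". It says nothing there about steroid. Section 5.3 says that the usual intramuscular steroid "represents a pragmatic approach to induce rapid suppression of inflammation".
- **Order of scan and treatment.** Protocol 9.3 requires the baseline scan to precede the start of study treatments. Section 9.4.3 has no order rule.
- **SAP.** Section 7.2.3 defines imaging remission as PD=0 at Week 24. Sections 11.6.5 and 11.6.6 summarise it descriptively. None of them mentions steroid given before the scan. The Week 24 analysis window in 11.2.2 runs from Day 128 with no upper limit.

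**The concern.** A patient can attend at Week 24, miss the DAS28ESR target, receive a steroid for that reason, and be scanned up to 7 days later, all within the protocol. The DAS28ESR and the scan then describe the patient on opposite sides of a steroid dose, yet both are reported as Week 24 status.

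This would matter little if such scans were spread evenly over the arms. They are unlikely to be, because the trigger is essentially the complement of the primary outcome: the arm with fewer remitters has more patients eligible for steroid at that visit. If steroid turns some positive scans into PD=0, the gain is larger in the poorer arm and the arms look more alike on imaging than they were at the visit.

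At stake is a named secondary endpoint, compared for A vs B and for B vs C. The protocol's own reasoning supports the worry: it stops NSAIDs so that inflammation remains detectable, and it describes the steroid as acting rapidly.

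**Working it through.** **Inputs.** Protocol 12.9 gives the planning rates. Among those with abnormal T-cell values it has "of whom 25% responded to MTX at 6 months compared to 68% of those with normal values", so remission is pA = 0.68 and pB = 0.25. The A:B ratio is k = 2.75, the variance inflation factor 1.05, two-sided alpha 5%, power 80%.

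**The plan's own figure.** The documents give no number for post-steroid scans. The sample size built on the same rates can be reproduced with the pooled-variance formula:

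- p̄ = (0.25 + 2.75 × 0.68)/3.75 = 0.565
- nB = [1.96·√(p̄(1−p̄)(1+1/k)) + 0.842·√(pB(1−pB) + pA(1−pA)/k)]² / (0.43)² = 13.32
- Total = 13.32 × 3.75 = 49.94; × 1.05 = 52.4, rounded up to the stated 53.

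So 68% and 25% are the working rates of the plan.

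**Step 1: who meets the trigger.** Non-remission is 1 − 0.68 = 32% in Arm A and 1 − 0.25 = 75% in Arm B. The ratio is 0.75/0.32 = 2.34. (Remission is defined as 2.6 or below and the steroid target as below 2.6; a score of exactly 2.6 is ignored here.)

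This is a per-patient ratio, not a ratio of counts. Expected non-remitters are 44 × 0.32 = 14.1 vs 16 × 0.75 = 12.0 at the smaller planned size, and 46 × 0.32 = 14.7 vs 30 × 0.75 = 22.5 at the larger.

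**Step 2: steroid for patients at target.** Let a share q of remitters also receive steroid because of synovitis, and assume all non-remitters do. The ratio of treated shares is (0.75 + 0.25q)/(0.32 + 0.68q):

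| q (assumed) | Ratio B:A |
|---|---|
| 0 | 2.34 |
| 10% | 2.00 |
| 25% | 1.66 |
| 50% | 1.33 |

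**Step 3: effect on the imaging difference (illustration).** Assume that PD=0 before steroid coincides with clinical remission. Let s be the share of non-remitters scanned after steroid and c the share of those who turn PD=0, both equal in the two arms. Then:

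- observed A = 0.68 + 0.32sc
- observed B = 0.25 + 0.75sc
- difference = 0.43(1 − sc)

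| s | c | Arm A | Arm B | Difference (points) |
|---|---|---|---|---|
| 0 | – | 68.0% | 25.0% | 43.0 |
| 25% | 10% | 68.8% | 26.9% | 41.9 |
| 50% | 25% | 72.0% | 34.4% | 37.6 |
| 100% | 50% | 84.0% | 62.5% | 21.5 |

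In the third row the Arm B gain is 0.75 × 0.125 = 9.4 points, or 1.5 patients out of 16. The last row is extreme: every non-remitter is treated and scanned afterwards.

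The text available for this review gives no planning remission rate for Arm C, so B vs C is not sized. If Arm C does better than Arm B, the same mechanism would narrow that difference too.

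**The case against.** **The endpoint is now only descriptive.** For A vs B, Protocol 12.3 said "two-tailed significance tests will be conducted at the 5% level of significance", but SAP 13.1 records that the imaging analyses were reduced to descriptive statistics. No test or model can be distorted. This stands and limits the weight of the point. It does not remove it: a reported percentage can still be biased, and with no model beside it, readers will take it at face value.

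**Steroid is part of treat-to-target care.** It is also allowed at baseline, Weeks 4 and 12, and unscheduled visits, with no washout before Week 24. A reader might infer that PD=0 after a Week 24 steroid is not remission on the first-line strategy. The documents do not go that far, since flare treatment belongs to the strategy. The narrower point survives: the scan and the DAS28ESR can fall on different sides of a dose that was prompted by that same DAS28ESR.

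**Post-steroid scans in Arm B need not be 2.3 times as frequent.** A reader might take 2.34 that way. It is a ratio of eligibility. It becomes a ratio of scans only if steroid goes solely to non-remitters, and uptake and scan timing are equal in both arms. Steroid is optional, patients at target may receive it, the window is symmetric around the visit, and clinicians know the T-cell result and treatment (Protocol 6.5.4), so uptake could differ by arm in either direction.

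**Baseline is not clearly open in the same way.** A reader might infer a similar gap from 9.3, which says "Offer IM/IA/PO corticosteroids as appropriate (in line with standard practice" at the baseline visit. But that section requires the scan before study treatments, which may well include steroid: the synopsis lists steroids among the non-investigational products, and 7.5.1 counts new steroid use as an intervention. Baseline imaging also does not define PD=0 at Week 24.

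**NSAID against steroid.** It is tempting to say that the plan withholds the weaker suppressor and allows the stronger. The documents do not rank the two.

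**Conclusion.** The gap is real. The plan, followed as written, permits a Week 24 scan up to 7 days after a steroid given because the Week 24 target was missed, and neither document orders the two or handles the result.

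On the planning rates, 32% of Arm A and 75% of Arm B would meet the trigger, a ratio of about 2.3 that falls if patients at target are also treated. With equal uptake, timing and conversion in the two arms, the bias shrinks the A–B imaging difference. Its size cannot be stated. The range from 41.9 down to 21.5 points, against 43, rests wholly on assumed values of s and c and on equating pre-steroid PD=0 with clinical remission. The protocol calls the steroid effect rapid but gives no time course.

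The point concerns a secondary, descriptive endpoint. It does not reach the DAS28ESR primary endpoint, which is not tied to the scan date. It is worth acting on because the remedy is cheap, not because the trial's main conclusion is at risk.

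**What to change.** **Protocol 9.4.3.** State that the Week 24 scan is done in the 7 days before the clinic visit, or on the same day before any corticosteroid given at that visit. The steroid rule itself stays as it is.

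**SAP 7.2.3, 11.6.5 and 11.6.6, for scans already collected.** Flag every Week 24 scan done after a steroid given at the Week 24 visit, and give the number by arm. Report imaging remission as observed and, as a sensitivity summary, with the flagged patients counted as not in imaging remission. The second version is deliberately conservative, since some of those patients may have been PD=0 before the steroid.

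**Cost.**
- Ultrasound booking becomes less flexible, and some scans may be missed. SAP 11.2.3 counts missing data as non-response in the main analyses, so missed scans would carry a cost of their own.
- The flag needs both dates. SAP 11.2.2 maps assessments by actual day, but the steroid items named in SAP 7.2.6 and Protocol 9.1 cover drug, type or route, and dose, not explicitly the date. Confirm that scan and steroid dates are recorded.
- Dates alone do not settle the order when scan and steroid fall on the same day; list those cases separately if no time was recorded.
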